**The minimum required patient count and site count 70 patients in one trial site.**

## 5.4 STUDY MEASURES

### 5.4.1 Primary effectiveness endpoint measures

The iTero 5D will be non-inferior to BWR in detecting the existence of primary interproximal caries lesions above the gingiva.

### 5.4.2 Secondary effectiveness endpoint measures

The iTero 5D will be non-inferior to BWR when comparing clinical findings during caries debridement

# Clinical Study Protocol 1

## 5.5 STATISTICAL ANALYSIS PLAN

Statistical tests will be performed to show comparison between iTero NIRI technology of the iTero Element 5D and bite-wing x-ray in detecting the existence of primary interproximal caries lesions above the gingiva

- Two-sided McNemar's Chi-square test to show if there is a statistically significant difference between the detection ability of the iTero NIRI technology of the iTero Element 5D and bite-wing x-ray
- Asymptotic Non-Inferiority test to show if the false positive (FP) rate ( $P_{10}$ ) is non-inferior than false negative (FN) rate ( $P_{01}$ ) with non-inferiority margin as 0.05, which means iTero NIRI technology of the iTero Element 5D is non-inferior than bite-wing x-ray in detecting primary interproximal caries
- One-sided binomial test to show if the false positive (FP) count ( $C_{10}$ ) is significantly higher than false negative (FN) count ( $C_{01}$ ), which indicates if iTero NIRI technology of the iTero Element 5D can detect more primary interproximal caries than bite-wing x-ray
- Kappa coefficient will be calculated to assess the agreement between two methods. (Moderate agreement (Kappa 0.41–0.60) is expected)

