## 4. STUDY DESIGN

### 4.1 OVERVIEW OF STUDY DESIGN

This is a non-significant risk, single site, prospective study to be conducted in the department of pediatric dentistry of the Hadassah Medical Center, Faculty of Dental Medicine, Hebrew University of Jerusalem, Israel. Subject participation will require one visit during which consent, screening, enrollment, and imaging will be performed. An additional follow-up call to the Investigator will take place a month later to review patient records and capture any clinical information recorded since last trial visit if a treatment was planned.

Each subject will be assigned a unique ID number that will link to their data. De-identified data sets will be used for analysis.

Clinical and diagnostic methods to be used during this study are those that are routinely used in the diagnosis of caries in this site, which include bitewing radiographs (BWR). This standard of care is provided for all site’s patients, including the patients who don’t participate in this clinical study.

A standard set of BWR for subjects ages 4-9 years will be taken to include the complete dentition of the subjects. Any recent bilateral BWR which were obtained up to 14 days prior to study visit may be used. **No additional x-ray should be taken for the sole purpose of this trial.**

In addition to the routine clinical diagnostics, the subjects will be scanned using the 5D system. The investigator will capture a full arch scan of the maxillary arch and mandibular arch of each subject with the iTero Element 5D system. For each subject, the Investigator will grade carious lesions in the BWR and Element intra-oral scan according to ADA staging guidelines. The results will be documented using

# Clinical Study Protocol 1

Caries Evaluation Forms. The Investigator will assess and document the findings of each diagnostic test separately before reviewing the next test.

In cases where caries debridement indicated, carious lesion depth will be documented during and compared to NIRI and BWR images. **All treatment decisions will be made according to the standard of care in the clinic and no treatment will be conducted for the sole purpose of the study.**

The study will include an interim analysis to assess the iTero Element 5D system useability among the first 20 pediatric subjects. Based on the findings' evaluation, modifications in the study protocol for the remaining 50 subjects will be considered.

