## 5. STATISTICAL AND ANALYTICAL PLANS

### 5.1 HYPOTHESIS

The test results can be summarized in the following 2x2 table:

	X-ray is the ground truth	
NIRI	Negative (no caries)	Positive (caries)
Negative (no caries)	$P_{00}$	$P_{01}$
Positive (caries)	$P_{10}$	$P_{11}$

Where  $P_{ij}$  = the percentage of tooth surfaces under certain condition out of all included surfaces.

As we are taking X-ray as the ground truth,  $P_{01}$  is the percentage of surfaces that can be detected as caries by X-ray but not NIRI (NIRI missed detection rate),  $P_{10}$  is the percentage of surfaces that can be detected by NIRI, but not X-ray (NIRI over detection rate). By showing that NIRI over detection rate ( $P_{10}$ ) is not less than NIRI missed detection rate ( $P_{01}$ ) by non-inferiority margin of  $M$ , we can conclude that NIRI is non-inferior than X-ray in detecting caries. Thus,  $P_{10}-P_{01}$  provides a measure for assessment of a non-inferiority between two procedures.

Null Hypothesis:  $P_{10}-P_{01} \leq -M$

Alternate Hypothesis:  $P_{10}-P_{01} > -M$

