### 5.2 ASSUMPTIONS

#### 5.2.1 Test results

By assuming:

1. 50% of the participants will have active caries
2. On average there are 1 carious surface per patient with active caries
3. there is minimum of 2 naïve IP surfaces per pediatric patient which may be captured in BWR

Approximately, out of all patients included in the trial, 1.8% of all tooth surfaces are carious and 98.2% of all tooth surfaces are non-carious.

# Clinical Study Protocol 1

Based on previous iTero 5D study, we can assume that for NIRI, the sensitivity for early enamel lesions is 0.51 and specificity is 0.90.

The assumed test results can be summarized as:

	X-ray is the ground truth	
NIRI	Negative (no caries)	Positive (caries)
Negative (no caries)	88.38%	0.88%
Positive (caries)	9.82%	0.92%

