## 5.3 SAMPLE SIZE

Sample size can be calculated from the sample size equation for comparing paired nominal data by using McNemar’s test:

$$n = \frac{[z_{\alpha}\sqrt{p_{01} + p_{10}} + z_{\beta}\sqrt{p_{01} + p_{10} - (p_{01} - p_{10})^2}]^2}{(p_{10} - p_{01})^2}$$

Similar formulae can be obtained for the one-sided non-inferiority test by substituting  $z_{\alpha/2}$ ,  $p_{10}$  with  $z_{\alpha}$  and  $p_{10} + M$ :

$$n = \frac{[z_{\alpha}\sqrt{p_{01} + p_{10} + M} + z_{\beta}\sqrt{p_{01} + p_{10} + M - (p_{01} - p_{10} - M)^2}]^2}{(p_{10} + M - p_{01})^2}$$

where significance level  $\alpha = 0.05$ , power  $1 - \beta = 0.8$ , non-inferiority margin  $M = 5\%$ , assumed detection rate  $p_{01} = 0.22\%$ ,  $p_{10} = 2.46\%$

The minimum sample size required is 89 surfaces. Assuming the drop off rate to be 30%, an additional 39 surfaces will be recruited, so the total number of surfaces needed for the clinical trial is 128. assuming a minimum of 2 naïve IP surfaces per paediatric patient.

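### The surface-level tests ignore correlation within a child; if it is positive, standard errors are too small and error rates exceed the nominal 5%

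*Combined protocol and SAP*

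**What the plan says.** - **Unit of analysis.** Section 5.1 defines each cell of the 2x2 table as "the percentage of tooth surfaces under certain condition out of all included surfaces". The hypotheses concern P10-P01 on that scale.
- **Sample size.** Section 5.3 derives 89 surfaces, adds 39 for drop-off and concludes that "the total number of surfaces needed for the clinical trial is 128". It turns this into children by "assuming a minimum of 2 naïve IP surfaces per paediatric patient". The enrolment target is 70 children.
- **Surfaces per child.** Two is a minimum; no maximum is given. Section 4.1 says "The investigator will capture a full arch scan of the maxillary arch and mandibular arch of each subject", and the bitewings are to cover the whole dentition. Section 5.2.1 also states that "1.8% of all tooth surfaces are carious and 98.2% of all tooth surfaces are non-carious".
- **Tests.** Section 5.5 lists a two-sided McNemar test, an "Asymptotic Non-Inferiority test to show if the false positive (FP) rate" is non-inferior to the false negative rate, a one-sided binomial test on the discordant counts, and kappa.

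Neither 5.3 nor 5.5 mentions within-child correlation, a design effect, a clustered variance, a GEE or mixed model, resampling by child, or a limit of one surface per child.

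**The concern.** The McNemar, non-inferiority and binomial tests all need independent pairs. Surfaces from one child share one scan, one set of radiographs and that child's cooperation. A poor scan, or a scan that invites over-calling, would shift the NIRI-minus-BWR difference the same way on several surfaces of that child. Positive correlation is therefore plausible, though the documents do not establish it.

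If it is present, the surface-level standard error of P10-P01 is too small. For the primary endpoint this error favours the device, because the lower confidence limit sits too high and the margin is cleared too easily. The binomial test, which is meant to support a claim that NIRI finds more caries than radiographs, is open to the same inflation.

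**Working it through.** **1. The plan's own figure.** Inputs from 5.3: p01 = 0.0022, p10 = 0.0246, M = 0.05, one-sided alpha 0.05, power 0.80.

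- p01 + p10 + M = 0.0768
- p10 + M - p01 = 0.0724, squared 0.005242
- n = [1.645 x sqrt(0.0768) + 0.842 x sqrt(0.0768 - 0.005242)]^2 / 0.005242 = 88.47, so 89
- 89 / 0.7 = 127.1, so 128

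Both stated figures reproduce from a formula for independent pairs. It contains no design effect.

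**2. Surfaces per child (m).** The stated minimum is 2. From 5.2.1, 50% of children with one carious surface each is 0.5 per child, and 0.5 / 0.018 = 27.8, so the 1.8% figure implies about 28. I add m = 8 as an assumed intermediate value.

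**3. Size by approximation.** The design effect is DE = 1 + (m - 1) x ICC. The true one-sided error of a nominal 5% test is about 1 - Phi(1.645 / sqrt(DE)).

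| m | ICC 0.05 | ICC 0.1 | ICC 0.2 |
|---|---|---|---|
| 2 | 5.4% | 5.8% | 6.7% |
| 8 | 7.8% | 10.4% | 14.4% |

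**4. Where the margin lies.** At m = 2 the planning prevalence is 0.5 / 2 = 25%. Section 5.2.1 assumes "the sensitivity for early enamel lesions is 0.51 and specificity is 0.90". Then P01 = 0.25 x 0.49 = 12.25%, P10 = 0.75 x 0.10 = 7.5%, and the difference is -4.75%, right beside the -5% margin. The boundary case P01 12.5%, P10 7.5% is thus close to the plan's own inputs. At m = 8 the prevalence is 0.5 / 8 = 6.25%, so P01 6%, P10 1% is a boundary case that fits it. Since P01 cannot exceed prevalence, the planning prevalence 0.5 / m puts the margin out of reach above m = 10. No non-inferiority error is quoted there.

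**5. Simulation.** Dirichlet-multinomial clusters, 70 children, 20,000-40,000 replicates per cell. The surface-level test uses variance [(P10 + P01) - (P10 - P01)^2] / (70m). The child-level test uses the variance of the 70 child-specific differences (t, 69 df). Type I error of the non-inferiority test at a nominal 5%:

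| m | P01 / P10 | Surface level, ICC 0 | Surface level, ICC 0.05-0.2 | Child level |
|---|---|---|---|---|
| 2 | 12.5% / 7.5% | 5.3% | 5.8-7.3% | 4.9-5.4% |
| 8 | 12.5% / 7.5% | 5.1% | 7.8-14.4% | 4.9-5.4% |
| 8 | 6% / 1% | 6.1% | 9.5-16.7% | 7.1-8.2% |

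Tests of no difference at P10 = P01 = 0.88% (the 5.2.1 value of P01), ICC 0.1:

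| m | McNemar, two-sided | Binomial, one-sided |
|---|---|---|
| 2 | no inflation | no inflation |
| 8 | 12% | 6% |
| 28 | about 31% | about 17% |

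The child-level test of no difference stayed at or below about 5%. Repeat runs moved these figures by at most about one percentage point.

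**6. Sample size.** If the 30% drop-off removes whole children, 70 x 0.7 = 49 remain. Effective surfaces are 49m / [1 + (m - 1) x ICC]. At ICC 0.1 this gives 98 / 1.1 = 89.1 (m = 2), 392 / 1.7 = 230.6 (m = 8) and 1372 / 3.7 = 370.8 (m = 28). At m = 2 the requirement is met up to an ICC of 98 / 88.47 - 1 = 0.108. At ICC 0.2 it falls to 98 / 1.2 = 81.7, where the plan's formula gives 77% power.

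**The case against.** The strongest reply has five parts.

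- **The correlation is assumed, and at two surfaces little happens.** This stands. At m = 2 the non-inferiority error is at most about 7% over the assumed range, and the tests of no difference are not inflated. The larger figures need 8 surfaces (my assumption) or 28 (implied by 5.2.1). But two is only a minimum, and nothing limits the analysis to two.
- **The plan's table is far from the margin.** The 5.2.1 table gives 9.82% - 0.88% = +8.94%. At those rates with correlation 0.2, surface-level and child-level tests both passed in every simulated trial. So if the table is right, the primary conclusion would not change. Type I error, however, concerns the case where the table is wrong. The bound 0.5 / m is likewise only a planning value. At m = 8 it would be reached at P01 6% only if NIRI missed 0.06 / 0.0625 = 96% of lesions, and the 12.5% / 7.5% case there needs twice the planned prevalence. The understated standard error remains wherever the true difference lies.
- **Power is not really threatened.** This largely stands. Section 5.3 applies drop-off to surfaces, and 4.4 allows withdrawn children to be replaced. If surfaces are lost at random across 70 children, correlation 0.2 leaves 86 effective surfaces and 79% formula power. At the 5.3 rates, simulated power with 49 children, two surfaces each and correlation 0.2 was above 99% for both tests. Extra surfaces do not repair a standard error that is too small.
- **One reader for all children adds no within-child correlation.** This is correct if a single investigator grades everything. The shared scan, radiographs and cooperation remain.
- **Section 5.5 gives no significance level for the McNemar and binomial tests.** Correct. The 5% in 5.3 belongs to the non-inferiority test, and 5% is assumed for the other two.

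**Conclusion.** The concern holds. As written, the plan gives standard errors that are too small whenever the signed discordance is positively correlated within a child, and no provision corrects this. Over an assumed correlation of 0.05-0.2, the primary test's type I error rises slightly at two surfaces per child and to roughly two or three times nominal at eight for correlations of 0.1-0.2. The tests of no difference can be badly inflated if all readable surfaces are analysed. These sizes rest on the assumed correlation, the assumed surface counts and the simulated error rates. The direction needs only positive correlation. Because the validity of the primary test is at stake, this should be settled before any data are analysed. It is a matter of error control; the effect on sample size is minor.

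**What to change.** - **Section 5.5:** name the child as the cluster and specify one child-level method for P10-P01, such as the Obuchowski or Durkalski variance for clustered matched pairs, or GEE with robust standard errors. Use it for the non-inferiority test and in place of the surface-level McNemar and binomial tests, and state the significance level of each. If an interval for kappa is reported, obtain it by resampling children.
- **Section 5.3:** state the assumed within-child correlation and number of surfaces per child, and say that the 80% power depends on both.

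The cost is SAP wording, a little programming and slightly wider intervals. Enrolment and data collection do not change. The remedy is not exact: with sparse false positives (eight surfaces, P01 6%, P10 1%) the child-level Wald test still ran at 7.1-8.2%. That is above 5% but below the 9.5-16.7% of the surface-level test.

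### Section 5.5 does not name the asymptotic statistic for the primary non-inferiority test; at 89 to 140 surfaces a Wald version would exceed the 5% one-sided level, while a score version stays close to it

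*Combined protocol and SAP*

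**What the plan says.** The primary endpoint (section 5.4.1) is non-inferiority of the scanner to bitewing radiographs. Section 5.1 expresses it as P10 − P01 > −M, where P10 and P01 are proportions of tooth surfaces.

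Section 5.5 lists three tests and a kappa coefficient. The primary hypothesis gets an "Asymptotic Non-Inferiority test to show if the false positive (FP) rate" is non-inferior to the false negative rate "with non-inferiority margin as 0.05". No statistic, variance estimator, confidence interval or alpha is given there. The other two tests are a "Two-sided McNemar's Chi-square test to show if there is a statistically significant difference" and a one-sided binomial test of whether C10 exceeds C01. The binomial test addresses superiority, not the margin.

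Section 5.3 sizes the trial for a one-sided non-inferiority test with alpha 0.05, power 0.8, M = 5%, p01 = 0.22% and p10 = 2.46%: "The minimum sample size required is 89 surfaces", raised to 128 for 30% loss. The target is 70 patients with at least two surfaces each. Section 5.2.1 tabulates different values for the same two cells, 0.88% and 9.82%.

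**The concern.** The word asymptotic covers several statistics that agree in large samples and differ in small ones. What matters for this hypothesis is the number of discordant surfaces, and at the section 5.3 rates only two to four are expected at the minimum surface count. The usual Wald statistic estimates its variance from those few surfaces. When few misses happen to occur, the variance estimate is too small and non-inferiority is declared too readily.

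The primary conclusion depends on this one test, and the other tests in section 5.5 do not address the margin. If the statistic is left open, the false non-inferiority rate is not controlled by the plan, and the choice could be made after the data are seen.

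**Working it through.** **1. Reproduce the plan's sample size.** Inputs from section 5.3: z(0.05) = 1.645, z(0.20) = 0.842, p01 = 0.0022, p10 = 0.0246, M = 0.05.

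- Sum: p01 + p10 + M = 0.0768. Difference: p10 + M − p01 = 0.0724.
- n = [1.645·√0.0768 + 0.842·√(0.0768 − 0.0724²)]² / 0.0724² = 88.47, rounded up to 89.
- 89 / 0.70 = 127.1, rounded up to 128.
- 70 patients × 2 surfaces = 140; 140 less 30% = 98.

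The plan's 89 and 128 both reproduce with one-sided alpha 0.05, so that is the level to hold the test to.

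**2. Expected discordant surfaces, n × (p01 + p10).**

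| Surfaces | Section 5.3 rates (2.68%) | Section 5.2.1 rates (10.70%) |
|---|---|---|
| 89 | 2.4 | 9.5 |
| 128 | 3.4 | 13.7 |
| 140 | 3.8 | 15.0 |

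These are counts under the assumed results. The error rate of the non-inferiority test is set on its null boundary, where P01 is at least 5%. Expected discordance there is at least 0.05 × 89 = 4.5 to 0.05 × 140 = 7.0.

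**3. The two statistics.** Let b be the count of surfaces positive on NIRI only, c the count positive on radiograph only, and d = (b − c)/n.

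- Wald: Z = (d + M) / √{[(b + c)/n − d²]/n}.
- Score: Z = (b − c + nM) / √{n(2q − M − M²)}, where q is the maximum-likelihood estimate of P01 under P10 = P01 − M.

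Both reject when Z > 1.645.

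**4. One case by hand: n = 89, P10 = 0, P01 = 5%, so b = 0.**

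- Wald at c = 2: d = −0.0225; Z = 0.0275 / √[(0.0225 − 0.0005)/89] = 1.75, which rejects. At c = 3 it does not.
- Score, with q at its limit of 0.05: the denominator is √(89 × 0.0475) = 2.056. At c = 2, Z = (4.45 − 2)/2.056 = 1.19, not rejected. At c = 1, Z = 1.68, rejected.
- Binomial(89, 0.05): P(c = 0) = 1.0%, P(c = 1) = 4.9%, P(c = 2) = 11.3%.
- Size: Wald P(c ≤ 2) = 17.2%; score P(c ≤ 1) = 5.9%.

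**5. Full enumeration** over all (b, c) on the boundary P10 − P01 = −5%. Surfaces are treated as independent, and a table with no discordant surface is counted as declaring non-inferiority.

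| Surfaces | Wald, P10 = 0 | Wald, P10 = 2.46% | Wald, P10 = 9.82% | Score, P10 = 0 | Score, P10 = 2.46% |
|---|---|---|---|---|---|
| 89 | 17.2% | 6.7% | 5.3% | 5.9% | 4.7% |
| 98 | 12.7% | 7.2% | 5.5% | 4.0% | 4.7% |
| 128 | 11.3% | 6.2% | 5.4% | 4.3% | 4.5% |
| 140 | 7.7% | 6.6% | 5.3% | 2.7% | 4.6% |

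Across P10 from 0 to 2.46% the score test stays within 2.7% to 5.9%.

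**The case against.** **The plan never says Wald.** This stands. A score test is equally asymptotic and holds close to 5%. The only formula shown, in section 5.3, puts p01 + p10 + M in its null term, and a test built on that variance would be conservative (size about 0.7% to 2.7% for P10 from 0 to 2.46%). A reader might infer that the planned test has the wrong error rate. The document supports only that its error rate depends on a choice it does not make.

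**The 17.2% is a corner case.** This also stands. It needs a scanner that never over-detects and only 89 surfaces. At the plan's own P10 values the Wald excess is 0.3 to 2.2 percentage points.

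**The sparse scenario is a floor.** Correct in part. The section 5.2.1 rates give about 10 to 15 discordant surfaces, and two surfaces per child is a stated minimum. With 0.5 carious surfaces per child, the 1.8% prevalence would imply 0.5/0.018, about 28 surfaces per child. But the sample size rests on the section 5.3 rates, and the plan commits to no count above the minimum.

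**McNemar's test.** A reader might infer that the large-sample chi-square also over-rejects here, since a 4–0 split gives p = 0.046 against an exact 0.125. The calculation does not support that. At 2.68% discordance the uncorrected chi-square has true size 2.0% at 89 surfaces and 3.9% at 140, both below 5%. The exact test would lower this to 0.1% to 0.4% and cut power at 140 surfaces from about 35% to 10% at the section 5.3 rates. There is no case here for replacing it.

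**Conclusion.** The point holds as a gap in specification for the primary test. At 89 to 140 surfaces, reading section 5.5 as a Wald test gives a one-sided size of 6.2% to 7.2% at P10 = 2.46%, and up to 17.2% at P10 = 0 with 89 surfaces. The score test gives 2.7% to 5.9% for P10 from 0 to 2.46%. If P10 is near 9.82% the choice hardly matters.

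The result rests on the minimum surface count, on the null boundary at the 5% margin, and on independent surfaces. The last does not match the design, since each child contributes two or more surfaces. The documents give no within-child correlation, so its effect is not quantified here; positive correlation would be expected to raise the size of any unadjusted version, score included.

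The conflict between the rates in sections 5.2.1 and 5.3 decides how sparse the data are expected to be, and it must be reconciled.

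**What to change.** In section 5.5, replace the generic asymptotic test with the restricted maximum-likelihood score test for paired proportions (Tango or Nam) and its matching confidence interval for P10 − P01. State one-sided alpha 0.05 and margin 0.05, and use a version that accounts for several surfaces per child. Reconcile the P01 and P10 values in sections 5.2.1 and 5.3, and restate the expected discordant count from the agreed rates. Leave McNemar's chi-square test as it is.

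The cost is a change of wording made before the data are analysed; it adds no subjects or procedures. The p-value will be slightly less favourable when discordance is sparse. At the section 5.3 rates and 89 independent surfaces, the power of the score test is 99.3% against 99.9% for Wald, so little is lost.

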## 5.2.2 Non- inferiority margin

Based on relevant literature and the results from previous trials, we can assume that the non-inferiority margin to be 5%.

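### The binomial test in section 5.5 reads an excess of NIRI false positives as NIRI detecting more caries; with X-ray as the reference it can show only that NIRI calls more surfaces positive.

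*Combined protocol and SAP*

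**What the plan says.** Section 5.1 sets the reference: "As we are taking X-ray as the ground truth". It defines P10 as the cell that "is the percentage of surfaces that can be detected by NIRI, but not X-ray (NIRI over detection rate"), and P01 as the NIRI missed-detection rate.

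Section 5.5 lists four analyses without ranking them. The third is a "One-sided binomial test to show if the false positive (FP) count ( $C_{10}$ ) is significantly higher than false negative (FN) count" (C01). A significant result is said to indicate whether NIRI "can detect more primary interproximal caries than bite-wing x-ray". No alpha is given for this test.

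Section 5.2.1 assumes that "1.8% of all tooth surfaces are carious and 98.2% of all tooth surfaces are non-carious" and that "the sensitivity for early enamel lesions is 0.51 and specificity is 0.90". Its assumed-results table has P10 = 9.82% and P01 = 0.88%. Section 5.3 sizes the trial with different rates, P10 = 2.46% and P01 = 0.22%.

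The stated objectives and endpoints (Study Summary, sections 3.1, 5.4.1 and 5.4.2) speak of comparison or non-inferiority. None of them states superiority.

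**The concern.** The hypothesis tested and the conclusion attached to it are different. The binomial test asks whether discordant surfaces fall equally in the two off-diagonal cells, that is, whether the two methods call the same number of surfaces positive. The conclusion is about how much caries is found. One bullet labels C10 surfaces false positives and also counts them as evidence of extra caries detected.

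If the bullet is followed as written, a significant result would be reported as NIRI detecting more caries than BWR when over-calling on sound surfaces could be the whole cause. Replacing the non-inferiority rule in the second bullet would not remove the problem, because this bullet carries its own conclusion.

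**Working it through.** **1. What the test can show.** Let prev be the share of carious surfaces by X-ray. Then:

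- P10 = (1 − prev) × (1 − specificity)
- P01 = prev × (1 − sensitivity)
- NIRI positive rate − BWR positive rate = (P10 + P11) − (P01 + P11) = P10 − P01

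The test therefore compares positive-call rates. Under the X-ray reference, lesions found by NIRI are in P11, and P11 cancels. In the section 5.2.1 table NIRI finds 0.92 of 1.80 percentage points of carious surfaces (51%), and BWR finds all of them by definition.

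**2. Reproducing the plan's figures.**

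- Section 5.2.1 cells: 0.982 × 0.10 = 9.82%; 0.018 × 0.49 = 0.88%. Both agree.
- Section 5.3 sample size, with one-sided alpha 0.05, power 0.80 and M = 0.05: the sum is 0.0022 + 0.0246 + 0.05 = 0.0768 and the difference is 0.0246 + 0.05 − 0.0022 = 0.0724. So n = [1.645 × √0.0768 + 0.842 × √(0.0768 − 0.0724²)]² / 0.0724² = 88.5, giving 89. Allowing for drop-off, 89 / 0.7 = 127.1, giving 128. Both agree.
- 70 children with the minimum of 2 surfaces each give 140 surfaces.

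**3. How often the test is significant.** The number of discordant surfaces m is Binomial(n, P10 + P01). Given m, C10 is Binomial(m, P10/(P10 + P01)). Reject when P(Binomial(m, 0.5) ≥ C10) ≤ alpha. Alpha is taken as one-sided 0.05, an assumption, and surfaces are treated as independent.

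| Inputs | P10 | P01 | n = 89 | n = 128 | n = 140 |
|---|---|---|---|---|---|
| Section 5.2.1 table | 9.82% | 0.88% | 79.6% | 93.8% | 95.8% |
| Section 5.3 rates | 2.46% | 0.22% | 5.8% | 17% | 20.7% |
| Prevalence 25%, sensitivity 0.51, specificity 0.90 | 7.5% | 12.25% | 0.2% | 0.1% | 0.1% |

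The 25% comes from reading the three numbered assumptions in section 5.2.1 literally, with exactly 2 surfaces per child: 0.5 × 1 / 2.

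The rows differ for simple reasons. At 89 surfaces the 5.2.1 table expects about 8.7 C10 and 0.8 C01 surfaces; a split of 9 to 1 gives p = 11/1024 = 0.011. The 5.3 rates expect only 2.2 and 0.2, while significance needs at least 5 discordant surfaces, all of them C10 (0.5⁵ = 0.031). At 25% prevalence misses are expected to exceed over-calls. At the plan's sensitivity and specificity, the two balance at prevalence 0.10 / (0.10 + 0.49) = 16.9%.

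**4. After the plan's own drop-off.** 128 × 0.7 = 89.6 and 140 × 0.7 = 98, so about 89 to 98 surfaces remain. On the 5.2.1 table the test is then significant in 79.6% to 84.3% of trials, or 69.5% to 75.6% at alpha 0.025.

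**5. A reader with no information.** Take sensitivity 0.10 and specificity 0.90, so that a positive call is equally likely on carious and sound surfaces. At 1.8% prevalence P10 = 9.82% and P01 = 0.018 × 0.90 = 1.62%. The test is significant in 67/85/89% of trials at 89/128/140 surfaces.

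**The case against.** Several points on the other side stand.

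- **The size is not settled.** A reader might infer from the 5.2.1 table that the conclusion would be drawn in 80% to 96% of trials. The documents do not support that as the single answer. The rates that actually size the trial give 6% to 21%, and 25% prevalence gives under 1%. The 94% and 96% figures also need no loss of surfaces, or more than the minimum of 2 per child.
- **The figures are not an inflated error rate.** It is tempting to set 80% against a nominal 5%. The null tested is C10 = C01, which is false on the 5.2.1 table, so the percentages are power.
- **A count of C10 merely above C01 does not trigger the conclusion.** The bullet requires C10 to be significantly higher.
- **A scanner that agrees perfectly with BWR never obtains the claim, but that is no defect.** Such a scanner should not be said to detect more.
- **No superiority objective or endpoint exists.** This is one of four unranked analyses. That the trial would go on to claim superiority formally is an inference; the documents provide only the sentence in this bullet.

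The strongest objection is that BWR is imperfect. Section 3.1 calls it common practice, so some C10 surfaces may be real lesions. On that reading the conclusion is unverified rather than impossible. It is still unsupported: no other reference is attached to this test, and excavation depth is a separate secondary measure recorded only where treatment was indicated.

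**Conclusion.** The conclusion attached to the third bullet of section 5.5 is wrong as written. With X-ray as ground truth, a significant result means that NIRI calls more surfaces positive; with BWR as an imperfect comparator, it leaves the extra calls unverified. Neither reading supports a statement that NIRI detects more caries. This follows from the plan's own definitions and needs no simulation.

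The frequency of the invalid conclusion ranges from under 1% to 96%, depending on which of the plan's conflicting inputs apply. With about 89 to 98 surfaces left after drop-off, it is 80% to 84% on the 5.2.1 table and 6% to 8% on the 5.3 rates. All these figures assume an exact one-sided test at 0.05 and independent surfaces; clustering within children is ignored.

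The bullet is not the primary endpoint, so this is a correction the plan should make rather than one that invalidates the trial.

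**What to change.** In the third bullet of section 5.5, keep the test and replace its conclusion with: *which indicates whether NIRI calls more surfaces positive than BWR; under the X-ray reference this excess is over-detection and supports no claim that NIRI detects more caries.* State the alpha for this test in the same place.

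If the excavation data listed among the CRFs in section 4.5 can be linked to individual surfaces, list any excavated C10 surfaces with their clinical finding, descriptively and with no inference from that treated subset. The documents do not say whether the data are recorded by surface, so this part is conditional.

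The change is to SAP wording and needs no additional patients. The sponsor gives up a statement about detecting more caries that the design cannot support.
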